2.3.2 Secondary Efficacy Objective

The secondary efficacy objective for this study is to make a preliminary assessment of the anti-neoplastic activity of atezolizumab administered in combination with Hu5F9-G4 to patients with R/R AML on the basis of the following endpoints:

- Objective response rate (ORR) achieved in the study, defined as the percentage of patients with a PR or better (i.e., CR+CRp+CRI+CRh+PR)
- Event-free survival (EFS), defined as the time from study entry to the date of induction treatment failure or relapse from CR, CRp, CRh, CRI, or death from any cause
- Leukemia-free survival (LFS), defined (only for patients achieving a CR, CRp, CRh, or CRI) as the time from the date of achievement of remission (CR, CRp, or CRI) until the date of relapse from CR, CRp, CRh, CRI, or death from any cause
- OS, defined as time from study entry to the date of death from any cause
- Progression-free survival (PFS), defined as the time from the first day of study treatment to disease progression or death, whichever occurs first
- Rate of transfusion independence, defined as the percentage of patients who achieve transfusion independence (i.e., achieving any continuous 56-day window without requiring platelet or RBC transfusions) at any time during study treatment

- Duration of transfusion independence, defined as the number of consecutive days of transfusion independence, measured from 1 day after the last transfusion to disease progression or subsequent transfusion

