4. MATERIALS AND METHODS

4.1 PATIENTS

A maximum of 21 patients with R/R AML will be enrolled in this study. The planned enrollment for dose safety is between 6 and 12 patients, depending on the DLTs observed. Enrollment of the expansion cohort will range between 9 and 15 patients. The overall enrollment of this study will remain constant at 21 patients.

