4.1.1 Inclusion Criteria

Patients must meet the following criteria for study entry:

- Signed Informed Consent Form
- Age ≥ 18 years at the time of signing Informed Consent Form
- Life expectancy of at least 12 weeks
- Eastern Cooperative Oncology Group (ECOG) Performance Status 0–2 (see [Appendix 4](#))

- Ability to comply with the study protocol, in the investigator's judgment
- Documented and confirmed R/R AML *per WHO classification*, except acute promyelocytic leukemia, *and lack of response to all therapies of known benefit*

Refractory AML is defined as failure to attain a CR following exposure to at least two courses of intensive induction regimens, six cycles of single-agent HMA, or at least two cycles of venetoclax-containing regimens (combined to LDAC or HMA).

Relapsed AML is defined as the morphological detection of $\geq 5\%$ bone marrow blasts, reappearance of leukemic blasts in the blood, or development of extramedullary disease. For patients previously found to be in CR and minimal residual disease (MRD) negative (by flow cytometry), reappearance of a leukemic population by MRD testing can be classified as being relapsed AML (conversion from CR MRD negative to CR MRD positive).

- Adequate end-organ function, defined using the following laboratory parameters obtained within 28 days prior to the first dose of study drug:

- AST, ALT, and ALP $\leq 2.5 \times$ upper limit of normal (ULN)
- Serum bilirubin $\leq 2 \times$ ULN, with the following exception:

Patients with known Gilbert disease or clear evidence of transfusion-related hemolysis who have serum bilirubin $\leq 3 \times$ ULN may be enrolled. Cases of transfusion-related hemolysis must be discussed and approved by the Medical Monitor.

- Serum creatinine $\leq 2 \times$ ULN

- Negative HIV test at screening
- Negative hepatitis B surface antigen (HBsAg) test at screening
- Negative total hepatitis B core antibody (HBcAb) test at screening, or positive total HBcAb test followed by quantitative hepatitis B virus (HBV) DNA < 500 IU/mL at screening

The HBV DNA test will be performed only for patients who have a positive total HBcAb test.

- Negative hepatitis C virus (HCV) antibody test at screening, or positive HCV antibody test followed by a negative HCV RNA test at screening

The HCV RNA test will be performed only for patients who have a positive HCV antibody test.

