4.5.6 AML and Response Evaluations

Any evaluable or measurable disease must be documented at screening and re-assessed at each subsequent cancer evaluation. Patients should have AML evaluation and classification based on the 2010 ELN and 2017 ELN criteria (see [Appendix 5](#)). Disease prognosis should also be classified at screening using the modified ELN risk classification (see [Appendix 5](#)). Responses will be assessed by the investigator through use of the ELN recommendations (see [Appendix 5](#)).

Bone marrow examinations must include aspirate and biopsy (whenever possible) for morphology, flow cytometry, and routine cytogenetic and are required at screening. If fluorescence in situ hybridization (FISH) is performed at screening, FISH must be

performed during subsequent assessments. Refer to Section 4.5.7.2 for timepoints and requirements regarding collection of required bone marrow samples (aspirates and trephine/core biopsies) for exploratory biomarker studies. Bone marrow aspirates and biopsies are to be performed on Day 22 of Cycle 1 and subsequently after 3 and 6 months of study treatment (i.e., Day 1 of Cycles 4 and 7; see [Appendix 1](#)). Beyond 6 months of study treatment, bone marrow aspirates are required within 7 days prior to study drug administration on Day 1 of every 3 months (i.e., Day 1 of Cycles 10, 13, 16, etc.) (for determination of response), at the time of relapse or progressive disease, and at the end of treatment. For patients in follow-up who discontinue study treatment prior to disease progression, bone marrow aspirates and biopsy should be collected every 4 months (see [Appendix 1](#)). All bone marrow examinations should be assessed locally (see Section 4.5.3). Local institutional policies should be followed at any other time during the study when a bone marrow examination is deemed necessary by the investigator.

In addition, information on transfusion requirements prior to and during study treatment will also be collected (see [Appendix 1](#)).

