6. STATISTICAL CONSIDERATIONS AND ANALYSIS PLAN

The primary analysis will be based on patient data collected through study discontinuation or the end of study. All analyses will be based on the safety-evaluable population, defined as all patients who receive any amount of either study drug.

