6.6 EFFICACY ANALYSES

Response assessment data (ORR, DOR, EFS, LFS, OS, PFS, the rate of transfusion independence, and the duration of transfusion independence) will be summarized for all patients as a single cohort. Time-to-event data will be summarized using Kaplan-Meier methods.

Interim looks may be performed during the study. Response data will be compared with the comparable historical data using statistical methodology such as a predictive and/or posterior probability design (Lee and Liu 2008), with the modification that the uncertainty in the historical control data is fully taken into account by utilizing a distribution on the control response rate to enable internal decision-making for future development. The possible data sources to be used as historical controls may be publications, real-world data sources, and other reliable information on efficacy from other studies in similar patient groups that will be available by the time of the interim analysis.

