6.6.2 Secondary Efficacy Endpoints

The secondary efficacy endpoints include ORR, EFS, LFS, PFS, OS, the rate of transfusion independence, and the duration of transfusion independence (see Section 2.3.2), which will be analyzed as follows:

- ORR will be assessed as the proportion of patients who obtain a CR, CRp, CRI, CRh or PR (as defined by the IWG 2003 and ELN 2010) after up to six cycles of combination therapy. The proportions will be calculated for categorical variables by dividing the number of patients with a positive response by the number of patients. Patients with no response assessments (for whatever reason) will be considered non-responders.
- For EFS, data from patients not known to have any of the listed events will be censored on the date they were last examined. For patients who do not achieve a CR, CRp, CRh, or CRI, EFS is defined as the point of progression or death, whichever comes first.
- For LFS, data from patients not known to have any of these events will be censored on the date they were last examined.
- For OS, data for patients who did not die will be censored at the date of last study visit or the last known date to be alive, whichever is later. If no postbaseline data are available, OS will be censored at the date of first treatment plus 1 day.
- Rate of transfusion independence is defined as the proportion of patients who achieve transfusion independence at any time during study treatment. Transfusion independence is defined as achieving any continuous 56-day window without requiring platelet or RBC transfusions.
- Duration of transfusion independence is defined as the number of consecutive days of transfusion independence, measured from 1 day after last transfusion to disease progression or subsequent transfusion.

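### The transfusion-independence rate ignores transfusion status at entry, and the duration endpoint does not say how a death is handled

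*Combined protocol and SAP*

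**What the plan says.** Section 2.3.2 defines transfusion independence as "achieving any continuous 56-day window without requiring platelet or RBC transfusions". Section 6.6.2 carries this into the analysis: "Rate of transfusion independence is defined as the proportion of patients who achieve transfusion independence at any time during study treatment". The denominator comes from Section 6: "All analyses will be based on the safety-evaluable population, defined as all patients who receive any amount of either study drug". Section 6.6 adds that the response data, with both transfusion endpoints listed among them, "will be summarized for all patients as a single cohort". None of these sections requires dependence at entry or splits the result by baseline status.

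Baseline data will exist. Section 4.5.6 states that "information on transfusion requirements prior to and during study treatment will also be collected", and Appendix 1 schedules a transfusion history at screening and a transfusion record during treatment. No analysis section uses the history.

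Duration of transfusion independence is a number of consecutive days, "measured from 1 day after last transfusion to disease progression or subsequent transfusion" (Section 6.6.2; Section 2.3.2 is the same in substance). Death is not among the end events and no censoring rule is given. DOR, PFS, EFS, LFS and OS all name death (Sections 2.3.1 and 2.3.2), and DOR, EFS, LFS and OS have censoring rules (Sections 6.6.1 and 6.6.2).

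**The concern.** The secondary efficacy objective is a first look at anti-leukemic activity. A rate that serves it should reflect patients who stop needing transfusions. As defined, it adds together two different things: conversion in patients who were dependent, and continuation in patients who were not. Only the first is direct evidence of benefit. With no control arm, the baseline contribution cannot be removed afterwards unless each patient's entry status has been classified.

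Patients who need no transfusions can enroll. No criterion in Section 4.1.1 requires dependence, and that section accepts relapse shown only by "conversion from CR MRD negative to CR MRD positive". Appendix 5 defines CR with recovered neutrophils and platelets, so such a patient may need no transfusions on Day 1.

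For duration, the gap is what the analyst does with a patient who dies while transfusion-free and without recorded progression. One permissible reading treats that patient as censored, that is, as someone who could have stayed transfusion-free for longer.

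**Working it through.** The plan states no target, expected rate or power for either endpoint, so there is no figure to reproduce.

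**Rate**

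Inputs from the documents:
- N = 21. Section 4.1 says: "The overall enrollment of this study will remain constant at 21 patients". This assumes all 21 are treated.
- Success is any 56-day window on treatment, with all treated patients as denominator.

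Assumed inputs, because the documents give none:
- b, the number transfusion independent at entry: 0 to 8 of 21.
- The share of those b patients who stay independent for 56 days: all or half.
- No drug effect, so no dependent patient converts.

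Formulas: the rate as written is x/21, where x is the number of the b patients who stay independent. The conversion rate among baseline-dependent patients is 0/(21 − b). Intervals are exact (Clopper-Pearson) 95%.

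| b | As written, all stay | As written, half stay | Conversion only (upper 95% limit) |
|---|---|---|---|
| 0 | 0/21 = 0% | 0/21 = 0% | 0/21 = 0% (16.1%) |
| 2 | 2/21 = 9.5% (1.2–30.4) | 1/21 = 4.8% | 0/19 = 0% (17.6%) |
| 4 | 4/21 = 19.0% (5.4–41.9) | 2/21 = 9.5% | 0/17 = 0% (19.5%) |
| 6 | 6/21 = 28.6% (11.3–52.2) | 3/21 = 14.3% | 0/15 = 0% (21.8%) |
| 8 | 8/21 = 38.1% (18.1–61.6) | 4/21 = 19.0% | 0/13 = 0% (24.7%) |

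What does not depend on the assumed b is the step: each baseline-independent patient who stays so adds 1/21 = 4.8 points.

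**Duration, if deaths were censored under Kaplan-Meier**

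Assumed inputs: constant hazards; a median of 4.0 months when death counts as an end event; and a share s of transfusion-free periods that end first in death, from 10% to 50%. None of these is in the documents.

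The total hazard is ln 2 / 4.0 per month. Censoring deaths leaves the fraction (1 − s) of it, so the Kaplan-Meier median becomes 4.0/(1 − s):
- s = 10%: 4.0/0.90 = 4.4 months (1.11-fold)
- s = 25%: 4.0/0.75 = 5.3 months (1.33-fold)
- s = 40%: 4.0/0.60 = 6.7 months (1.67-fold)
- s = 50%: 4.0/0.50 = 8.0 months (2.0-fold)

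A simulation of 200,000 periods agreed at s = 25% (5.33) and s = 50% (8.02). If only qualifying periods are analyzed, each lasts at least 56 days by definition. The multiplier then applies only to the time beyond day 56, and the inflation of the whole period is smaller.

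**The case against.** Four arguments against the point carry weight.

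- **The number of baseline-independent patients may be small.** Section 4.1.1 limits entry to patients whose disease has not responded to every therapy of known benefit. Section 1.4 calls Grade 3 anemia common at baseline in this disease. Section 5.1.2 lists anemia as an expected effect of Hu5F9-G4 and describes frequent red-cell and platelet support. Staying transfusion-free for 56 days on this drug is therefore less likely than off it. This limits the size of the effect but does not cure the definition.
- **A reader might infer that the plan censors deaths and so lengthens the estimated duration.** The documents do not say that. Section 6.6.2 defines the measure as a count of days. Section 6.6 applies Kaplan-Meier to time-to-event data without saying whether this count is one of them. If it is summarized as a day count, a patient who dies simply stops accruing days and nothing is lengthened. What stands is that the handling of death is unspecified.
- **The weight is limited.** This is one of seven secondary endpoints in a single-arm Phase Ib study that Section 6.1 says was not sized on power or type I error. Primary efficacy rests on CR rate and DOR, and deaths are counted in five other endpoints. This stands. Section 6.6 does foresee comparing response data with historical data for internal decisions, but it does not say whether the transfusion endpoints will be included. If they were, a rate that depends on the mix at entry would be hard to interpret.
- **The baseline split is not free.** No look-back period is given for the transfusion history, and screening spans Days −28 to −1, shorter than the 56-day window. This stands and belongs in the fix.

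**Conclusion.** The rate is mis-specified for its stated purpose: it credits treatment with transfusion independence that was already present at entry. The inflation is 4.8 points for each such patient who stays independent, with 21 treated. It would be wrong to read the table as an estimate that the rate will be overstated by 5 to 19 points, or by as much as 38. Those figures rest wholly on assumed baseline numbers and persistence, and the documents' own remarks on anemia point toward the lower end, possibly to zero.

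The duration endpoint is incompletely specified. Upward bias follows only if deaths without progression or transfusion are censored under Kaplan-Meier. The 1.11- to 2.0-fold range is conditional on that choice and on an assumed share of deaths.

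Both gaps should be closed before the data are analyzed. Neither touches the primary safety or efficacy conclusions.

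**What to change.** In Sections 2.3.2 and 6.6.2:

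1. Define baseline transfusion dependence from the history collected at screening, with a stated look-back window. A 56-day look-back would match the endpoint but reaches beyond the 28-day screening period, so the case report form must ask for it.
2. Beside the overall rate, report conversion (denominator: dependent at baseline) and maintenance (denominator: independent at baseline), each as a count with an exact interval. Section 6.7 already makes this kind of separation for anti-drug antibodies.
3. Add death from any cause as an end event for duration.
4. Start duration no earlier than the first dose for patients never transfused on study. For them, the day after the last transfusion may precede treatment or not exist.
5. State whether duration is analyzed by Kaplan-Meier or summarized as a day count, and give a censoring rule for patients still transfusion-free at last assessment.

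The cost is analysis-plan wording, one derived baseline variable and possibly one added data-collection instruction. With 21 patients the two subgroups will be small and their intervals wide, and the headline figure may fall.

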2.4 IMMUNOGENICITY OBJECTIVE

The immunogenicity objective for this study is to evaluate the immune response to atezolizumab and Hu5F9-G4 on the basis of the following endpoints:

- Incidence of ADAs against atezolizumab during the study relative to the prevalence of ADAs at baseline
- Incidence of ADAs against Hu5F9-G4 during the study relative to the prevalence of ADAs at baseline

2.5 EXPLORATORY BIOMARKER OBJECTIVE

The exploratory biomarker objective for this study is to identify biomarkers that are predictive of response to atezolizumab in combination with Hu5F9-G4 (i.e., predictive biomarkers), are associated with progression to a more severe disease state (i.e., prognostic biomarkers), are associated with acquired resistance to atezolizumab and/or Hu5F9-G4, are associated with susceptibility to developing adverse events, can provide evidence of atezolizumab and/or Hu5F9-G4 activity, or can increase the knowledge and understanding of disease biology on the basis of the following endpoints:

- Relationship between biomarkers in blood and bone marrow (including somatic mutations) (listed in Section 4.5.7.2) and efficacy, safety, PK, immunogenicity, expression profiles, bone marrow aspirate stromal factors, or other biomarker endpoints
- To determine the effect of single agent Hu5F9-G4 on T-cell activation and bone marrow infiltration in patients with R/R AML

3. STUDY DESIGN

3.1 DESCRIPTION OF THE STUDY

This is a Phase Ib, open-label, multicenter, non-randomized study of atezolizumab, evaluating the safety and pharmacokinetics of atezolizumab (an anti-PD-L1 monoclonal antibody) given in combination with Hu5F9-G4 (an anti-CD47 monoclonal antibody) for the treatment of patients with R/R AML (excluding promyelocytic leukemia).

An initial safety evaluation will be performed in 6 patients with relapsed AML. If atezolizumab in combination with Hu5F9-G4 is found to be initially safe and tolerable in patients with R/R AML, an additional cohort of 15 patients with R/R AML will be evaluated to further test the safety and anti-tumor activity of atezolizumab in combination with Hu5F9-G4.

[figure not shown]
If DLTs are observed in $\geq 33\%$ of patients (i.e., 2 or more of 6 patients) in this initial safety cohort, a dose de-escalation cohort of 6 patients will be enrolled. If $< 33\%$ of the enrolled (1 patient or no patients) and dosed patients in any given cohort experience a

DLT, an expansion cohort of 15 patients will be enrolled at the higher tolerated dose for this combination. If a dose de-escalation cohort is needed (n=12 for safety cohorts), an expansion cohort of 9 patients will be enrolled at the lower tolerated dose for this combination. The maximum number of patients enrolled in this study will be 21 patients (this number will include patients assessed for DLT plus those potentially removed prior to DLT assessment).

3.1.1 Overview of Study Design

[Figure 1](#) presents an overview of the study design. A schedule of activities is provided in [Appendix 1](#).

Figure 1 Study Schema

Atezo=atezolizumab; DLT=dose-limiting toxicity; Q2W=every 2 weeks; QW=once a week.

Note: On days when both atezolizumab and Hu5F9-G4 are administered (Day 22 of Cycle 1 and Days 8 and 22 of subsequent cycles), Hu5F9-G4 should be administered first and *the interval between Hu5F9-G4 and atezolizumab infusions should follow guidelines as outlined in [Table 2](#).*

The proposed treatment regimen during Cycle 1 is a biomarker-driven treatment plan designed to assess the effect of single-agent Hu5F9-G4 on markers of immune activation in AML. This safety cohort is designed to assess the safety, tolerability, and clinical activity of Hu5F9-G4 in combination with atezolizumab based on the following schedule:

- Atezolizumab: Atezolizumab will be administered to patients by IV infusion at a fixed dose of 840 mg, starting on Day 22 of Cycle 1. In subsequent cycles (Cycles 2 and beyond), 840 mg of IV atezolizumab will be given every 2 weeks (Q2W) on Days 8 and 22 of each 28-day cycle.
- Hu5F9-G4: Two priming doses of 1 mg/kg of Hu5F9-G4 will be administered to patients by continuous IV infusion on Days 1 and 4 of Cycle 1, followed by loading doses of 15 mg/kg IV on Day 8 and 30 mg/kg IV on Day 11. Starting on Day 15 of Cycle 1, Hu5F9-G4 maintenance will be given by IV infusion at a dose of 30 mg/kg once a week (QW) of each 28-day cycle. On days when both atezolizumab and Hu5F9-G4 are administered (Day 22 of Cycle 1 and Days 8 and 22 of subsequent cycles), Hu5F9-G4 should be administered first and *the interval between Hu5F9-G4 and atezolizumab infusions should follow guidelines as outlined in Table 2*.

If DLTs are observed in $\geq 33\%$ of patients (i.e., 2 or more of 6 patients) in this initial safety cohort, a dose de-escalation cohort of 6 patients will be enrolled. The dosing schedules for this de-escalation cohort will be as follows:

- Atezolizumab will be administered to patients by IV infusion at a fixed dose of 840 mg, starting on Day 22 of Cycle 1. In subsequent cycles, 840 mg of atezolizumab administered by IV infusion will be given Q2W on Days 8 and 22 of each 28-day cycle.
- Hu5F9-G4 will be given as two priming doses of 1 mg/kg IV on Days 1 and 4, followed by loading doses of 10 mg/kg IV on Day 8 and 15 mg/kg on Day 11. Starting on Day 15, maintenance treatment with Hu5F9-G4 will be given by IV infusion at a dose of 15 mg/kg QW.
- If $<33\%$ (i.e., 1 or fewer of 6 patients) *patients in the de-escalation cohort experience a DLT*, an expansion cohort of 9 patients will be enrolled to further test the safety and anti-tumor activity of atezolizumab in combination with Hu5F9-G4, using the same dosing regimen

If DLTs are observed in $<33\%$ of patients (i.e., 1 or fewer of 6 patients) in the initial safety cohort, an expansion cohort of 15 patients will be enrolled to further test the safety and anti-tumor activity of atezolizumab in combination with Hu5F9-G4, using the same dosing regimen.

Study treatment will be administered until unacceptable toxicity or loss of clinical benefit, as determined by the investigator, after local biopsy results (if available) and clinical status (e.g., symptomatic deterioration such as pain secondary to disease) are assessed.

